## SUMMARY

**Rationale:** During Endoscopic Ultrasound (EUS), tissue samples can be obtained with different techniques. Fine needle aspiration (FNA) provides a cytological specimen. With fine needle biopsy (FNB), a histological specimen is obtained, which generally results in a better diagnostic performance. However, FNB needles are stiffer and more difficult to handle, and can therefore result in less tissue acquisition.

**Objectives:** To compare the performance and diagnostic accuracy of two EUS-guided tissue acquisition devices; a 25G Echotip Ultra Fine Needle Aspiration (FNA) device and a new, more flexible 20G Echotip ProCore Fine Needle Biopsy (FNB) device.

**Study design:** International randomized multicenter trial.

**Study population:** Patients  $\geq 18$  years old, referred for EUS-guided tissue sampling of a: (I) pancreatic mass lesion, (II) lymph node, or (III) other submucosal or undefined mass (non-pancreatic),  $\geq 1$  cm in size.

**Intervention:** EUS-guided tissue acquisition by means of either the 25G Echotip Ultra FNA device, or the 20G Echotip ProCore FNB device.

**Main study parameters/endpoints:** The main endpoint is the diagnostic performance, measured against the *gold standard* diagnosis (based on the surgical resection specimen or in non-operated patients, the outcome of the diagnostic work-up (i.e. tissue sampling and imaging studies), confirmed by a compatible clinical disease course). Secondary endpoints include I. technical success, II, specimen specifics, such as; quality, presence of tissue cores, and pathological classification (cytology, cell-block, or histology), III. procedural aspects, such as; safety, the yield of a single needle pass, and the value of on-site pathological evaluation, and IV. inter-observer variation.

**Nature and extent of the burden and risks associated with participation, benefit and group relatedness:** There are no additional risks involved. Patients are referred for EUS-guided tissue acquisition, as part of the standard diagnostic work-up. Previous reports showed EUS-guided FNA and FNB sampling to be equally safe.

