### **I.2 Univariate analysis**

#### **I.2.1 Primary endpoint**

Overall diagnostic accuracy will be compared between the two groups, using the Pearson's chi-squared test. Additionally, the p-value, adjusted by strata, will be calculated.

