### **I.3 Multivariate analysis**

To study the effect of the two methods on the different outcome measures, additional multivariate analysis will be applied, as described below.

Logistic regression will be applied to assess differences of accuracy between the two methods, adjusted for; age, indication, number of needle passes, vial number, and the presence of an on-site pathologist.

Ordinal logistic regression will be applied to assess differences of quality and presence of tissue cores between the two methods, adjusted for; age, indication, number of needle passes, vial number and the presence of an on-site pathologist.

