#### **I.4 Analysis Population**

All analysis will be performed on an intention-to-treat (ITT), modified ITT, and per protocol population. The ITT population are patients that were randomised in the study. The modified ITT population is defined as all patients in whom a puncture resulted in the collection of a diagnostic tissue sample. Patients in which a puncture resulted in tissue collection, independent of the quality of the sample (diagnostic or not) are defined as the per protocol population.

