#### **I.6 Missing Data**

Missing data will be reported, evaluated, and corrected if possible. When more than 30% of a variable is missing, the interpretation of this variable, as well as exclusion of this variable from the analysis, will be considered carefully. Prior to closure of the database, an official statistical analysis plan will be written.

Filename: Statistical plan ASPRO protocol.doc  
Directory: /Users/[name]/Dropbox/ASPRO/METC EMC/C. Protocol  
Template: /Users/[name]/Library/Group Containers/UBF8T346G9.Office/User  
Content.localized/Templates.localized/Normal.dotm  
Title: Instructions for use 'Template Research Protocol'  
Subject:  
Author: [name]  
Keywords:  
Comments:  
Creation Date: 2/24/20 10:20:00 AM  
Change Number: 2  
Last Saved On: 2/24/20 10:20:00 AM  
Last Saved By: [name]  
Total Editing Time: 0 Minutes  
Last Printed On: 2/24/20 10:20:00 AM  
As of Last Complete Printing  
Number of Pages: 5  
Number of Words: 755 (approx.)  
Number of Characters: 4.309 (approx.)

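### Does letting the study sample feed the gold standard in non-operated patients require a change to the accuracy analysis?

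*Protocol*

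**What the plan says.** The Protocol Summary (main study parameters/endpoints) sets the gold standard in two parts. For operated patients it is "based on the surgical resection specimen or in non-operated patients" the alternative applies: "the outcome of the diagnostic work-up (i.e. tissue sampling and imaging studies), confirmed by a compatible clinical disease course". In its paragraph on burden and risks, the Summary adds: "Patients are referred for EUS-guided tissue acquisition, as part of the standard diagnostic work-up". The sampling under study is therefore part of the work-up whose outcome serves as reference.

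SAP I.2.1 states that "Overall diagnostic accuracy will be compared between the two groups" by Pearson's chi-squared test, with a further p-value adjusted by strata. SAP I.3 adds a model: "Logistic regression will be applied to assess differences of accuracy between the two methods, adjusted for; age, indication, number of needle passes", together with vial number and on-site pathologist. SAP I.4 repeats the analyses in three populations, one of them being "all patients in whom a puncture resulted in the collection of a diagnostic tissue sample". None of these uses the route by which the final diagnosis was established. SAP I.6 announces a further document: "Prior to closure of the database, an official statistical analysis plan will be written".

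**The concern.** When the test under evaluation contributes to its own reference, some of its errors are scored as correct. This is incorporation bias. Here it could occur when the sample gives a wrong diagnosis, the patient is not operated on, and the later course happens to fit that wrong diagnosis. Accuracy would then be overstated in both arms.

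The between-needle difference is the result that matters. It would shrink if one needle gives more wrong diagnoses and carry-over is equal. A false difference could appear if carry-over differed between needles. Because the gold standard defines the primary endpoint and no listed analysis looks at its source, a reader of the trial report might be unable to tell whether this had happened.

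**Working it through.** The documents contain no figure to reproduce: the supplied text gives no sample size, power, accuracy rate or share operated. Everything below is an illustration on assumed inputs.

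**Inputs (all assumed).** Share not operated q = 0.7; 200 patients per arm; true accuracy 80% versus 90%; a non-diagnostic sample counts as not accurate. In each arm, w is the share with a wrong diagnosis, nd the share non-diagnostic, and r the chance that a wrong diagnosis is taken into the gold standard of a non-operated patient.

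**Formula.** Apparent accuracy = 1 − w − nd + w·q·r. Only w is multiplied by r, so a non-diagnostic sample carries nothing over. Power is the normal approximation for two proportions, pooled null variance, two-sided 5%. Without carry-over it is 80.2%.

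**Equal carry-over in both arms**

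| Failures | r | Apparent accuracy | Gap (points) | Power |
|---|---|---|---|---|
| All wrong: w 20% vs 10% | 0.10 | 81.4% vs 90.7% | 9.3 | 77% |
| same | 0.25 | 83.5% vs 91.75% | 8.25 | 71% |
| same | 0.50 | 87.0% vs 93.5% | 6.5 | 59% |
| Few wrong: w 2% vs 1%, rest non-diagnostic | 0.50 | 80.7% vs 90.35% | 9.65 | 78.5% |
| w 5% in each arm, rest non-diagnostic | 0.50 | 81.75% vs 91.75% | 10.0 | 84% |

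Example for the third row: 1 − 0.20 + 0.20 × 0.7 × 0.5 = 0.870 and 1 − 0.10 + 0.10 × 0.7 × 0.5 = 0.935. For the fourth: 0.80 + 0.02 × 0.35 = 0.807 and 0.90 + 0.01 × 0.35 = 0.9035. When w is the same in both arms, the added term w·q·r is the same, so the gap does not move at any r.

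**Unequal carry-over, no true difference.** Let both arms be truly 80% accurate, with r = 0.10 in one and 0.30 in the other. The false gap is w × 0.7 × 0.20.

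- w = 20% (all failures wrong): 2.8 points; the test rejects 11.5% of the time.
- w = 10%: 1.4 points; 6.5%.
- w = 5%: 0.7 points; 5.4%, against a nominal 5%.

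The documents neither support nor exclude a difference in r between the needles.

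**Which failures does the plan expect?** On biopsy needles in general, the Rationale says that they "can therefore result in less tissue acquisition". That points to failed or scanty samples, the kind that carries nothing over. It does not establish the mix in this trial, whose biopsy device is described as more flexible.

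**What an analysis without the study sample would give.** With 80% versus 90%, the 95% CI half-width is 1.96 × √(0.25/m), where 0.25 = 0.8 × 0.2 + 0.9 × 0.1.

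- All patients (m = 200): 6.9 points.
- With 10% to 30% indeterminate (m = 180 to 140): 7.3 to 8.3 points.
- Resected patients only (m = 200 × 0.3 = 60): 12.7 points.

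With no bias at all, the shift between the resected subset and the full comparison has a standard error of √(0.25/60 − 0.25/200) = 5.4 points. It would exceed 3.5 points in 52% of trials by chance.

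**The case for a change.** The strongest case for a change is that the planned analyses cannot reveal carry-over. Only w(1 − q·r) is observable. Wrong diagnoses of 20% versus 10% with r = 0.50 leave 0.20 × 0.65 = 13% and 0.10 × 0.65 = 6.5% visible. True rates of 13% and 6.5% with no carry-over look identical, in both the intention-to-treat and the modified population, although the true gaps are 10.0 and 6.5 points. The supplied text also gives no follow-up length and no criteria for a fitting clinical course, so the strength of that safeguard cannot be judged. A table by arm of how each diagnosis was reached would be inexpensive.

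The identification argument stands, and so does the remark about follow-up, although only a summary of the protocol is available and its body may set such rules. What does not follow is that a further prespecified analysis would repair this. The table is descriptive and changes no estimate; analysts can add it under the SAP still to be written. Setting the study sample aside requires assessors to re-judge every non-operated patient across an international multicentre trial, which is far more than one rerun. It then keeps only patients whose diagnosis can be settled by other means. A failed or doubtful sample may itself lead to more tissue or to surgery, so membership of that subset may differ by arm. The result could depart from the primary one with no incorporation bias, or agree with it despite some.

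**Conclusion.** The reading of the documents is right: the study sample is not excluded from the gold standard in non-operated patients, and no planned accuracy analysis uses the source of that standard. It does not call for a change.

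On the assumed inputs (70% not operated, 200 per arm, 80% versus 90%), the effect of equal carry-over on the difference runs from nil, when wrong diagnoses are equally common in both arms, to a loss of 3.5 points. That worst illustrated case needs every failure to be a wrong diagnosis and half of the wrong diagnoses in non-operated patients to survive follow-up. With few wrong diagnoses (2% versus 1%), the loss is at most 0.35 points over r up to 0.50. A false difference needs carry-over to differ between needles, for which the documents give no evidence.

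Against this, the reference already demands confirmation by the clinical course, uses resection where there is one, and applies alike to both arms. Resection cannot be had in every patient, so a composite reference is the reasonable choice. The available alternative has selection problems of its own and less precision, and it leads to no different decision; statisticians could fairly disagree on whether to run it. Reporting how final diagnoses were reached is sensible practice that needs no amendment.

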## **I. STATISTICAL ANALYSIS**

### **I.1 Descriptive statistics**

Depending on distributional properties, outcome measures will be expressed as means  $\pm$  standard deviations (SD) or as medians with interquartile ranges (IQR). Missing follow-up data will be considered to be missing at random. Statistical significance will be assessed with the use of Student's t-test for normally distributed continuous data; either the chi-square test for categorical data (with Yates' correction when appropriate) or Fisher exact test for categorical data; and the median test for non-normally distributed continuous data. Data will be analysed with SPSS, Statistical Package for the Social Sciences. SPSS Inc, Chicago, Illinois.

### **I.2 Univariate analysis**

#### **I.2.1 Primary endpoint**

Overall diagnostic accuracy will be compared between the two groups, using the Pearson's chi-squared test. Additionally, the p-value, adjusted by strata, will be calculated.

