#### **I.2.2 Secondary endpoints**

Technical success, pathological classification on which diagnosis was based, and safety (i.e. adverse events) will be compared between the two arms, using the Pearson's chi-squared test. Additionally, the p-value, adjusted by strata, will be calculated. Differences in quality and the presence of tissue cores of both arms will be tested using the non-parametric test for ordinal outcomes. Kappa values will be calculated to determine inter-observer variability among pathologists.

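### The primary comparison of accuracy leads with an unadjusted Pearson test; the strata-adjusted test the plan already computes would be the better single primary test, for a modest gain in precision

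*SAP*

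**What the plan says.** SAP section I.2.1 gives the primary endpoint two p-values: "Overall diagnostic accuracy will be compared between the two groups, using the Pearson's chi-squared test. Additionally, the p-value, adjusted by strata" is to be calculated as well. The order suggests that Pearson leads, but the plan does not say so. The method of adjustment is not named.

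Three other places bear on which result decides:

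- Section I.4: "All analysis will be performed on an intention-to-treat (ITT), modified ITT, and per protocol population". The first set is everyone randomised. The other two are defined by what the puncture yielded: a diagnostic sample for modified ITT, any tissue for per protocol. None is called primary.
- Section I.1, in a general list of tests, allows "either the chi-square test for categorical data (with Yates' correction when appropriate) or Fisher exact test for categorical data".
- Section I.3 adds a logistic model for accuracy, "adjusted for; age, indication, number of needle passes, vial number, and the presence of an on-site pathologist".

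On possible strata, the protocol summary describes an "International randomized multicenter trial" and lists the eligible lesions as "I) pancreatic mass lesion, (II) lymph node, or (III) other submucosal or undefined mass (non-pancreatic". The supplied text does not say which factors, if any, stratified the randomisation. They may be defined in text not supplied, so this is not counted as a defect.

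**The concern.** If the strata predict accuracy and allocation was balanced within them, the arms are more alike than Pearson's variance assumes. The test then rejects less often than its nominal level and gives up some power. The stratified analysis recovers this and is already planned, but only in second place.

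The logistic model in I.3 does not fill that role. It includes indication, but it also adjusts for the number of needle passes, which are made after allocation, so it is not a plain comparison of the randomised arms.

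A smaller matter is that, with no test or population named as deciding, the choice can be made after the results are known.

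**Working it through.** **Inputs.** The supplied text states no sample size, accuracy, effect, alpha or strata, so there is no figure of the plan to reproduce. Everything below is an illustration. Assumed: two-sided 5%, 1:1 allocation, three strata (equal, or 50/25/25), 400 or 600 patients, common odds ratio 1.8 for power.

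**Step 1: size of Pearson under balanced allocation.** With stratum shares w, accuracies p and overall accuracy p̄, the ratio of the true null variance to the variance Pearson uses is

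R = Σ w·p(1−p) / [p̄(1−p̄)], and the size is P(|Z| > 1.96/√R).

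- 90/80/70%, equal strata: Σ = (0.09 + 0.16 + 0.21)/3 = 0.1533; p̄(1−p̄) = 0.80 × 0.20 = 0.16; R = 0.958; size = P(|Z| > 2.002) = 4.5%.
- 95/75/50%, strata 50/25/25: Σ = 0.5 × 0.0475 + 0.25 × 0.1875 + 0.25 × 0.25 = 0.1331; p̄(1−p̄) = 0.7875 × 0.2125 = 0.1673; R = 0.796; size = P(|Z| > 2.197) = 2.8%.

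**Step 2: power, CMH without continuity correction minus Pearson, by simulation.** The power ranges cover both sample sizes, both sets of weights, and balanced, blocked and simple allocation.

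| Control accuracy by stratum | R (weights) | Pearson size, balanced | Power difference, points |
|---|---|---|---|
| 80/80/80% | 1.000 (any) | 5.0% | −0.8 to 0.0 |
| 85/80/75% | 0.990 (equal) | 4.9% | −0.3 to +0.3 |
| 90/80/70% | 0.958 (equal) | 4.5% | +0.8 to +1.6 |
| 92/75/55% | 0.881 (equal) | 3.7% | +3.0 to +5.5 |
| 95/75/50% | 0.796 (50/25/25) | 2.8% | +5.0 to +8.5 |

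In patients, at 80% power with balanced allocation, CMH needs 2–3% fewer at 90/80/70% and 10–12% fewer at 95/75/50%.

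**Step 3: a second set of assumptions.** Strata 50/25/25, balanced allocation, +10 points overall, 600 patients. CMH against Pearson: 88.6 vs 88.5% at 80/75/70%, 89.8 vs 88.9% at 85/75/60%, 90.9 vs 88.4% at 90/70/50%. Under the null, for 200 to 800 patients, CMH stayed at 4.9–5.1% throughout.

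**Step 4: conditions on the gain.**

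- *Continuity correction.* A corrected CMH lies 3.7–6.2 points below uncorrected Pearson at flat 80%, and 2.5–4.9 below at 90/80/70%. At moderate spread the gain exists only without correction.
- *Many small strata.* With 30 assumed strata and simple randomisation, CMH on all 30 loses about 2 to 3.5 points at flat 80% and about 0.5 to 2 at 90/80/70%. With blocks within the 30 strata the difference is only −0.4 to +1.4. With 39 strata balanced by allocation and 600 patients, CMH had 86.2% against 85.2% for Pearson.

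**Step 5: taking the smaller of the two p-values.** With allocation balanced or blocked within three strata the type I error stays at about 5%. Under simple randomisation it is 5.8–6.2% at 90/80/70%. Either test named alone stays at about 5% or below.

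**The case against.** The strongest reply is that the plan already ranks its tests: accuracy is compared by Pearson, and the adjusted p-value is an extra. Pearson is valid, and naming either test would settle the matter, so preferring CMH is a choice and not a correction. That largely stands. What remains is that the more efficient of two analyses, both already planned, sits in second place.

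Two further points stand in full. The power gains of three points or more need accuracy to fall to 55% or 50% in one stratum, which nothing in the documents supports. And the general remark on Yates' correction in I.1 is reasonably overridden by I.2.1, which names Pearson's test for this endpoint.

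A reader might infer three stronger claims.

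- *That the plan inflates the type I error.* Two tests in three populations give 2 × 3 = 6 p-values, and taking the smallest gives 9.4–12.3% under assumed rates. But Pearson alone across the three populations already gives 8.9–10.8%. That is a matter of unranked populations and says nothing about Pearson against CMH.
- *That lesion type should be the stratum.* The protocol summary lists lesion types as eligibility and does not call them randomisation strata.
- *That I.2.2 needs the same change, with exact stratified tests.* Section I.2.2 has the same construction ("Technical success, pathological classification on which diagnosis was based, and safety (i.e. adverse events) will be compared between the two arms"). But for sparse adverse events (assumed 0.5–2% per arm) the exact stratified test has size 0.0–2.4%, while asymptotic CMH at 1.3–4.6% already stays below 5%. It would give up power and correct no demonstrated error.

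Finally, SAP section I.6 promises a formal SAP before the database is closed. It may settle the ranking, but it is not available here.

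**Conclusion.** The point holds as an optional improvement. I.2.1 puts the unadjusted test ahead of a stratified one that is already planned, and neither the test nor the population is named as deciding. The loss is about 0 to 1.5 power points at flat to moderate spread in accuracy, and larger only if the strata are strongly prognostic. It is not a validity error: Pearson's size is at or below about 5% in every scenario.

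All figures rest on assumed sample sizes, accuracies, effects and strata. The conservatism in step 1 also requires allocation balanced within strata, which the supplied text neither states nor excludes. Confidence is medium.

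**What to change.** In I.2.1, or in the formal SAP promised in I.6:

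1. Name one primary test: Cochran-Mantel-Haenszel without continuity correction, using the strata of the randomisation, listed by name. Pool very small strata if allocation was not balanced within them. Confirm that the statistic taken from SPSS, the package named in I.1, is the uncorrected one.
2. Run it in all randomised patients, which is the ITT set in I.4. State in advance one rule for patients without a sample or without a reference diagnosis. I.1 and I.6 speak only of missing data in general.
3. Report the stratum-adjusted risk difference with 95% CI.
4. Label Pearson's test and the other two populations as sensitivity analyses.

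No new data are needed. Most of this is a few lines; the rule in item 2 takes more thought, but any analysis of all randomised patients needs one. The statistical price is under one power point if a few strata prove not to be prognostic.

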#### **I.2.2 Secondary endpoints**

Technical success, pathological classification on which diagnosis was based, and safety (i.e. adverse events) will be compared between the two arms, using the Pearson's chi-squared test. Additionally, the p-value, adjusted by strata, will be calculated. Differences in quality and the presence of tissue cores of both arms will be tested using the non-parametric test for ordinal outcomes. Kappa values will be calculated to determine inter-observer variability among pathologists.

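### The safety comparison is planned as p-values only; it should report the risk difference between needles with a 95% confidence interval

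*SAP*

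**What the plan says.** The Protocol summary lists safety as a secondary endpoint, among the procedural aspects. The main endpoint is diagnostic performance. The needle under test is "a new, more flexible 20G Echotip ProCore Fine Needle Biopsy (FNB) device". The paragraph on burden and risk says that participation adds no risk and gives as background: "Previous reports showed EUS-guided FNA and FNB sampling to be equally safe".

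SAP section I.2.2 sets the safety analysis: "safety (i.e. adverse events) will be compared between the two arms", by Pearson's chi-squared test. It continues: "Additionally, the p-value, adjusted by strata, will be calculated".

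Three other SAP sections bear on this:

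- Section I.1 allows, in general, "either the chi-square test for categorical data (with Yates' correction when appropriate) or Fisher exact test for categorical data". The summaries it names are means with SD and medians with IQR, neither of which suits a yes/no event.
- Section I.3 plans regression models for accuracy, specimen quality and tissue cores. It plans none for safety.
- Section I.4 says: "All analysis will be performed on an intention-to-treat (ITT), modified ITT, and per protocol population". The safety tests are therefore repeated in three populations.

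The supplied text names no risk difference, confidence interval or safety margin for adverse events.

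**The concern.** Each planned safety comparison ends in a p-value. A test of no difference can give evidence of a difference, but a result above 0.05 is not evidence of similarity. With few events it is compatible with anything from a benefit to a material excess, and the p-value alone does not show which. The further options (adjustment by strata, Yates, Fisher, three populations) add p-values, not estimates.

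This matters because the 20G needle is described as new, so reports on FNA and FNB in general do not settle its own risk. This trial will produce randomised data on that question. Readers will set its safety result beside the background statement in the Protocol summary. Without an estimate and interval, they cannot see how large an excess the data leave open.

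**Working it through.** **Inputs.** The supplied text gives no sample size, allocation ratio, significance level or adverse event rate, so there is no planned figure to reproduce. Assumptions: 1:1 allocation, n = 100 to 400 per arm, two-sided 5% level, and a rate of 1% or 2% with the 25G needle. The test (Pearson chi-squared) is from I.2.2.

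**Step 1: chance of detecting an excess.** With a and b events in arms of size n, and m = a + b, the uncorrected Pearson statistic is

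X² = (a − b)² × 2n / [m(2n − m)],

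and the test rejects when X² > 3.84. Power is the sum of the binomial probabilities of all pairs (a, b) that reject.

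| n per arm | 1% vs 2% | 2% vs 4% | 1% vs 3% | 1% vs 5% |
|---|---|---|---|---|
| 100 | 5.6% | 11.4% | 14.2% | 37.2% |
| 200 | 11.5% | 21.0% | 27.8% | 68.5% |
| 300 | 15.8% | 30.2% | 42.4% | 86.4% |
| 400 | 19.2% | 38.4% | 52.7% | 94.2% |

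For a doubling, the chance of a non-significant result runs from 100 − 38.4 = 61.6% (2% vs 4%, 400 per arm) to 100 − 5.6 = 94.4% (1% vs 2%, 100 per arm). Fisher's test gives lower power: 9.0% instead of 15.8% for 1% vs 2% at 300 per arm. By the usual approximation, 80% power needs 2319 per arm for 1% vs 2% and 1141 for 2% vs 4%.

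**Step 2: what a non-significant p-value can conceal.** Suppose 6/300 events with 20G FNB and 3/300 with 25G FNA.

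- X² = 3² × 600 / (9 × 591) = 5400 / 5319 = 1.02, p = 0.31.
- Risk difference: 2.00 − 1.00 = +1.00 percentage point.
- Wilson 95% limits: 0.92 to 4.29% for 6/300 and 0.34 to 2.90% for 3/300.
- Newcombe lower limit: 1.00 − √[(2.00 − 0.92)² + (2.90 − 1.00)²] = −1.18 points.
- Newcombe upper limit: 1.00 + √[(4.29 − 2.00)² + (1.00 − 0.34)²] = +3.39 points (from unrounded Wilson limits).

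The p-value says not significant. The interval says that an excess of up to 3.4 points, over an observed 1% with the 25G needle, remains open.

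**Step 3: what the interval would look like in general.** The Newcombe half-width with equal observed counts, in percentage points:

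| n per arm | 1% rate | 2% rate | 5% rate |
|---|---|---|---|
| 100 | 4.5 | 5.2 | 6.8 |
| 200 | 2.7 | 3.3 | 4.6 |
| 300 | 2.0 | 2.5 | 3.6 |
| 400 | 1.7 | 2.1 | 3.1 |

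**Step 4: could the test raise a false signal?** With 4/300 versus 0/300, X² = 16 × 600 / (4 × 596) = 4.03, p = 0.045. With Yates' correction, 9 × 600 / (4 × 596) = 2.27, p = 0.13; Fisher gives p = 0.12. The expected count is 2 events per arm, a setting in which one would turn to the I.1 options, and neither gives a signal. Over the assumed range the Pearson test's false-positive rate is 1.4–4.9%. Error control is not the problem.

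**The case against.** The strongest reply has four parts.

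1. **Low power for rare events comes from trial size, not from the test.** This is correct. An interval uses the same counts and detects nothing more. What it adds is a statement of what the data exclude, and the p-value does not supply that.

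2. **The power figures rest on assumed inputs.** Also correct. A reader might infer that the safety test will almost always be non-significant, or that the trial can neither support nor refute similar safety. The documents do not support either reading. Under the same assumptions a rise from 1% to 5% is detected with 86% power at 300 per arm and 94% at 400. At 400 per arm a tripling of 1% is detected about half the time.

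3. **The plan makes no claim of equal safety.** A reader might infer that the trial rests on that premise. It does not: the remark is background, attributed to earlier reports, and the objective is diagnostic performance. Nor does the plan say that p > 0.05 will be read as equal safety. The risk is a misreading that the plan does nothing to prevent.

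4. **The text is brief and not final.** Section I.2.1 names no interval for the primary endpoint either, section I.6 promises an official SAP before database closure, and only a summary of the Protocol is available. Safety definitions or a sample size may exist elsewhere. This limits the severity. But I.2.2 does state a method for safety, and a better one costs almost nothing, so the point stands.

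**Conclusion.** The point holds as a reporting defect in a secondary endpoint: safety is to be judged by p-values alone, with no estimate or interval. Assuming 100 to 400 per arm, a 1–2% base rate and a two-sided 5% level, a true doubling would go undetected in about 62–94% of trials. A non-significant result would then say little about the relative safety of the new needle. A large excess could still be found.

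The Pearson test is not invalid here, and the 4-versus-0 example does not show a false-signal problem, because I.1 permits the corrected and exact tests. The size of the power problem depends wholly on the assumed inputs. The absence of a planned estimate and interval in the supplied text does not.

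**What to change.** In I.2.2, or in the official SAP promised in I.6, take safety out of the list of outcomes judged by chi-squared and write:

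*Adverse events will be reported as counts and rates per arm. The main safety result is the risk difference (20G FNB minus 25G FNA) with a two-sided 95% Newcombe interval. P-values are descriptive, using Fisher's exact test or Yates' correction when expected counts are small, as I.1 allows. A non-significant p-value will not be reported as equal safety. Any statement of comparable safety will quote the upper confidence limit for the excess risk.*

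The same text should state what counts as an adverse event, unless the full protocol already does. It should also say which I.4 population carries the main safety result; of the three, only ITT keeps patients from whom no tissue was collected. The strata-adjusted p-value can stay as a descriptive addition.

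A change to the risk paragraph of the Protocol summary is optional, because its statement is already attributed to previous reports.

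Cost: a few lines of SAP text and one more column in the adverse event table, from counts that will be collected anyway. The small downside is a less favourable safety statement, since the interval will probably show that a moderate excess cannot be excluded.
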